#### **9.2.1.4 End of DB2 Period (Visit 4); End of Treatment (or Early Termination)**

- Confirm the following:
  - V4 is to be within 2 to 7 days after treatment of a migraine attack with study drug dispensed at V3 (not applicable to ET)
  - From randomization, the total duration of subject's participation in the study would be up to 10 weeks from baseline
- Review/collection of AEs
- Physical examination (if warranted); suicidality check
- Weight of subject
- Vital signs measurement (sitting SBP/DBP, pulse rate, and body temperature)
- Urine pregnancy test for female subjects of childbearing potential
- Blood draw for hematology and clinical chemistry, including HbA1c
- Urine collection for urinalysis
- Urine drug test and ethanol screen
- 12-lead ECG

- Concomitant medication review, including from eDiary entries
- Confirm subject compliance and study drug accountability
- Review, confirm, and ensure proper recording of eDiary entries by subject
- Collection of eDiary; empty study drug containers, and all unused study drug

#### **9.2.1.4.1 Efficacy Assessments**

Subjects will be provided with an eDiary at screening (V1) to collect at least 1 migraine attack during the screening period. The migraine episode may be treated with medication the subject currently uses for a migraine during this period, unless otherwise instructed by the Investigator. After at least 1 migraine attack has been recorded in the eDiary, as instructed, the subject will contact the study site to schedule Visit 2 (V2). At V2 (randomization), it will be determined if subjects meet all study requirements and are eligible to continue in the study. If a subject does not meet all requirements, they must return all study equipment that was provided at the Screening Visit. If randomized, subjects will continue to collect migraine data (for a migraine attack treated with study drug), study drug, last food intake and fat content, and any rescue medication used to treat a migraine. Subjects will record migraine predose assessments, study drug date and time taken, and postdose efficacy data in real time in the 2 DB periods through V4/ET:

- Level of headache pain at predose and at various time points postdose (Levels: 0 = none; 1 = mild; 2 = moderate; 3 = severe)
- Time to meaningful pain relief (based on subject's perception) and time to pain-freedom after study drug
- Migraine symptoms and MBS other than pain: nausea, photophobia, and phonophobia at predose and at various time points postdose; allodynia
- Functional disability at predose and at various time points postdose; scale: 0 = no disability, able to function normally; 1 = performance of daily activities mildly impaired, can still do everything but with difficulty; 2 = performance of daily activities moderately impaired, unable to do some things; 3 = performance of daily activities severely impaired, cannot do all or most things, bed rest may be necessary
- Treatment satisfaction (7-point scale)
- PPMQ-R

MBS will also be collected during Screening via Migraine History evaluation and this Screening MBS will be used for the evaluation of the second co-primary endpoint.

#### **9.2.2 Safety Assessments**

Safety assessments to be performed ([Table 9-1](#)) include the following:

- AEs will be collected from signing of the informed consent form (ICF) at screening (V1) until subject's completion or discontinuation from the study
- Concomitant medication review
- Physical examinations and suicidality check
- Pregnancy tests in female subjects of childbearing potential
- Measurement of vital signs (sitting SBP/DBP, pulse rate, and body temperature)
- Clinical laboratory examination (hematology, chemistry, and urinalysis)
- 12-lead ECG

Visits may be scheduled as needed for AE management. Adverse event and concomitant medication review should be performed at each unscheduled visit. Any protocol-specified safety assessment may be repeated or conducted unscheduled as necessary to ensure subject safety.

#### **9.2.2.1 Physical Examination and Suicidality Check**

A complete physical examination will be performed at screening (V1) by the Investigator, or medically qualified designee, and will include examination of the head, eyes, ears, nose, and throat [HEENT], heart, lungs, abdomen, skin, cervical and axillary lymph nodes, neurological, and musculoskeletal systems. All findings will be kept in the source document. At all subsequent visits, symptom-driven limited physical examination will be performed and recorded. Any subsequent untoward change during the study will be recorded as an AE. In addition, medical history will be recorded at screening, including smoking history, if applicable.

A suicidality check will be performed at screening (V1), baseline (V2), and at all other visits. In the event a subject is evaluated to be at risk at V1 or V2, in the opinion of the Investigator, the subject will be excluded from the study. A randomized subject will be discontinued if a significant suicide risk is determined at subsequent visits. At any visit, subjects who are found to be a suicide risk will be referred to a mental health specialist. The Medical Monitor should also be notified.

#### **9.2.2.2 Pregnancy**

All female subjects of childbearing potential will be required to undergo a serum pregnancy test (hCG) at screening (V1), and a urine pregnancy test (beta hCG) at all subsequent study visits. All subjects confirmed to be pregnant at any time during the study should be immediately discontinued. Female subjects of childbearing potential will be required to use an acceptable form of birth control from screening through the end of participation in the study. Although pregnancy is not an SAE, the procedures to report pregnancies will be the same as the procedures detailed for reporting SAEs ([Section 9.2.2.7](#)). Any pregnancy that occurs in a female subject (or female partner of a male subject) during the study, or within 30 days after taking the last dose of study drug, should be reported to [name] as described in [Section 9.2.2.7](#). Pregnancies will be followed to the end, whether successful live birth or premature termination, type and date of delivery, any congenital malformations or birth defects, or any other adverse fetal or neonatal outcomes, and reported on a follow-up Pregnancy Report. Sponsor will be notified of all the above pregnancy outcomes. Pregnancy will not be considered an AE.

Male subjects (with female partner) must agree to practice a reliable form of contraception or abstinence during the study.

#### **9.2.2.3 Clinical Laboratory Evaluation**

The following clinical laboratory evaluations will be performed in accordance with assessment time points outlined in [Table 9-1](#).

Hematology	Serum chemistry	Urine analysis (dipstick)
Hematocrit (Hct) Hemoglobin (Hb) Glycosylated hemoglobin (HbA1c) Mean corpuscular hemoglobin (MCH) Mean corpuscular hemoglobin concentration (MCHC) Mean corpuscular volume (MCV) Platelet count Mean platelet volume Red blood cell (RBC) count Red cell distribution width White blood cell (WBC) count with differential (absolute/percent basophil count, absolute/percent eosinophil count, absolute/percent lymphocyte count, absolute/percent monocyte count, absolute/percent neutrophil count)	Albumin Alanine aminotransferase (ALT) Alkaline phosphatase (ALP) Aspartate aminotransferase (AST) Creatinine Creatine kinase Electrolytes (bicarbonate, calcium, chloride, magnesium, phosphorus, potassium, sodium) Thyroid-stimulating hormone (TSH) Total bilirubin Direct bilirubin Total protein Urea nitrogen Uric acid	Color Appearance Specific gravity pH Protein Glucose Ketones Bilirubin Indicators of blood Urobilinogen Nitrite Leukocyte esterase Automated microscopic examination upon abnormal flagging
Serology tests: Human immunodeficiency virus (HIV), hepatitis B surface antigen (HBsAg), and hepatitis C virus (HCV) antibody analyses		
Urine drug and ethanol screen tests: ethanol, amphetamines, barbiturates, benzodiazepines, cocaine, opiates (including methadone), and tetrahydrocannabinoids (THC), and phencyclidine		
Pregnancy test: Serum pregnancy test will be performed on all female subjects of childbearing potential at screening visit (or at any other time during the study if needed to confirm a suspected pregnancy after a positive urine pregnancy test). A urine pregnancy test will be performed onsite at other time points for all female subjects of childbearing potential.		
Hematology (including HbA1c), clinical chemistry, and urinalysis may be repeated during the study as needed to evaluate a patient's condition. Tests not specified in the protocol may be allowed after discussion with the Sponsor's Medical Monitor or designee.		

Hematology (including HbA1c), TSH, clinical chemistry, urinalysis, urine drug test/ethanol screen, serum pregnancy tests, HIV, HBsAg, and HCV antibody analyses will be performed at the central laboratory (ACM Global Central Laboratory, [name]). Reference ranges will be supplied by the central lab and will be used by the Investigator to assess the laboratory data for clinical significance and pathological changes.

#### 9.2.2.4 Vital Signs

Vital signs, including pulse rate, sitting SBP/DBP, and body temperature, will be collected at screening (V1) and at each study visit. Vital signs will be recorded after the subject has rested in the sitting position for 5 minutes. (See additional exclusion criteria for SBP/DBP screenings in [Section 6.3.1](#)).

Blood pressure measurements are to be taken in the same arm for the duration of the study. Body weight (without shoes) will be recorded at screening and V4/ET, and height (without shoes) will be recorded at screening only.

Start and stop dates of last menstrual cycle for all female subjects of childbearing potential will be recorded at screening and at each study visit.

Vital sign measurements will be repeated if clinically significant per the Investigator's judgment or if machine/equipment errors occur. Out-of-range blood pressure, pulse rate, and body temperature measurements will be repeated at the Investigator's discretion. Any confirmed clinically significant vital sign measurement in the Investigator's opinion must be recorded as medical history or an AE, as applicable.

#### **9.2.2.5 Twelve-Lead Electrocardiogram**

A 12-lead resting ECG will be performed at screening (V1), and at every scheduled study visit, and will be reviewed initially by the Investigator for any immediate concerns, and then by a central reader, [REDACTED]

[REDACTED] At screening, the Investigator will examine the ECG tracings for signs of cardiac disease that could exclude the subject from the study. ECGs will be repeated if clinically significant abnormalities are observed or artifacts are present. [REDACTED] will provide ECG reports to the sites and [REDACTED] via a portal. With the exception of QTcF evaluation as specified in [Section 6.3.1](#), the overall interpretation and determination of the clinical relevance of ECG findings will be the responsibility of the Investigator, taking into account the central reader's evaluation, and will be recorded in the subject's eCRF.

#### **9.2.2.6 Adverse Events**

##### **Adverse Event Definition**

An AE is defined as any untoward medical occurrence in a clinical study subject administered a study drug and which does not necessarily have a causal relationship with this treatment. A TEAE is an AE with a start date on or after the initial dose of study drug and up to 5 days after the last dose of study drug. An AE can therefore be any unfavorable and unintended sign (including an abnormal laboratory finding), symptom, or disease temporally associated with the use of the study drug, whether or not related to the study drug. This includes an exacerbation of pre-existing conditions or events, intercurrent illnesses, drug interaction, or the significant worsening of the indication under investigation that is not recorded elsewhere in the eCRF. Anticipated fluctuations of pre-existing conditions, including the disease under study, that do not represent a clinically significant exacerbation or worsening need not be considered AEs.

**Migraine headaches will not be captured as AEs.** Migraine headaches will be captured by the subject in the eDiary provided to them.

For the purpose of the site's data collection responsibilities, any untoward event that started or worsened after the ICF was signed until the final end-of-study visit (inclusive) is to be considered an AE.

It is the responsibility of the Investigator to document all AEs that occur during the study. Adverse events will be elicited by asking the subject a non-leading question, for example, "Have you experienced any new or changed symptoms since we last asked/since your last visit?" Adverse events should be reported on the appropriate page of the eCRF.

***Assessment of Severity***

Each AE will be assigned a category by the Investigator as follows:

Mild	An AE that is easily tolerated by the subject, causes minimal discomfort, and does not interfere with everyday activities.
Moderate	An AE that is sufficiently discomforting to interfere with normal everyday activities; intervention may be needed.
Severe	An AE that prevents normal everyday activities; treatment or other intervention usually needed.

If there is a change in severity of an AE, it must be recorded as a separate event.

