### 6.2.5. Treatment Emergent Adverse Events

A TEAE for DB1 is defined as an AE that started on or after the first dose of study drug (DFN-15 or placebo) in DB1 or any existing AE that worsens in severity on or after the date of the first dose of study drug in DB1 up to 5 days after the date of the last dose of study drug in DB1 or up to taking DB2 study drug, whichever occurs first.

A TEAE for DB2 is defined as an AE that started on or after the first dose of study drug (DFN-15 or placebo) in DB2 or any existing AE that worsens in severity on or after the date of the first dose of study drug in DB2, up to 5 days after the date of the last dose of study drug in DB2.

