### **9.3. ADVERSE EVENTS**

All AEs will be coded using the Medical Dictionary for Regulatory Activities (MedDRA; version 19.0 or higher). Migraine headaches will not be captured as AEs. Migraine headaches will be captured by the subject in the eDiary provided to them, and the information will be entered into the appropriate eCRF page.

All AEs will be listed by subject. The following listings of AEs will be provided:

- All AEs
- Study-drug related AEs
- Serious adverse events (SAEs)
- AEs leading to death
- Adverse events leading to study-drug termination

Only TEAEs will be included in summary tables. Summaries for AEs will be presented for the SS, SS1, and SS2. An overall summary table of TEAEs will be produced for the following categories:

- Any TEAE
- Study-drug related TEAEs
- Serious TEAEs
- TEAEs leading to study-drug termination
- TEAEs leading to death

All TEAEs will be classified by system organ class (SOC) and preferred term (PT). Frequency count and the number of unique subjects of a TEAE will be tabulated by treatment(s) received. For the number of unique subjects reporting, if a subject reported more than one AE that was coded to the same SOC or PT, the subject will be counted only once for that specific SOC or PT.

The following summaries of TEAEs will also be provided:

- TEAEs by SOC and PT
- Study-drug related TEAEs by SOC and PT
- Serious TEAEs by SOC and PT
- TEAEs by maximum severity (mild, moderate, severe or missing) by SOC and PT
- TEAEs by strongest causality relationship (not related, possibly related, probably related, definitely related or missing) by SOC and PT

For TEAEs presented by relationship to study treatment(s), the strongest relationship to study treatment(s) during the study will be presented for each subject if coded to the same SOC or PT. For TEAEs presented by severity, the worst severity during the study will be presented for each subject if coded to the same SOC or PT. TEAEs with missing causality will be counted as related. TEAEs with missing severity will be counted as severe. The same will be true in the individual summaries.

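### Every change in AE severity, improvement included, opens a separate event, and no rule stops these split records from being counted as additional TEAEs

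*Protocol*

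**What the plan says.** **Recording.** Under Assessment of Severity, protocol 9.2.2.6 states: "If there is a change in severity of an AE, it must be recorded as a separate event". The instruction is mandatory and is not confined to worsening. The list of data to document for each AE (same section) includes severity and the date of first occurrence. It does not say which start date a record opened for a severity change should carry, or how that record is tied to its parent.

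**Protocol TEAE definition.** Sections 9.2.2.6 and 10.5.6 use the start date alone: "A TEAE is an AE with a start date on or after the initial dose of study drug", up to 5 days after the last dose.

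**SAP TEAE definition.** Section 6.2.5 works by period and has two limbs joined by *or*. The first is by start: "A TEAE for DB1 is defined as an AE that started on or after the first dose of study drug". The second covers "any existing AE that worsens in severity on or after the date of the first dose of study drug in DB1". The DB2 definition has the same structure; its first limb is "defined as an AE that started on or after the first dose of study drug (DFN-15 or placebo) in DB2". The window runs to 5 days after the dose and, for DB1, closes earlier if the DB2 dose is taken first.

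**Tabulation.** SAP 9.3: "Frequency count and the number of unique subjects of a TEAE will be tabulated by treatment(s) received". A subject is counted once per system organ class or preferred term, and the severity tables use the worst grade. No rule links or collapses records that belong to one episode.

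**The concern.** The recording rule and the TEAE definition assume different data structures. SAP 6.2.5 reads as if each AE were one record whose severity may change. Protocol 9.2.2.6 produces a chain of records, one per severity level. When the definition is applied record by record, a record that exists only because an AE got milder can satisfy the start-date limb, although nothing new happened and nothing worsened.

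The proportion of subjects with TEAEs is a listed secondary endpoint (protocol 10.4.2, SAP 4.2 and 8.2.1), and the TEAE tables are the main safety output of a two-arm trial. Subjects are re-randomized between periods, so a record assigned to the wrong period may also be assigned to a different treatment. If sites can date a split record either way, its TEAE status depends on site habit.

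**Working it through.** The plan gives no figure to reproduce, so the check applies the rules to each possible history.

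**Inputs**
- Severity scale: mild, moderate, severe (protocol 9.2.2.6). A mild AE that eases has resolved and opens no new record.
- AEs are collected from consent (protocol 9.2.2), so some can be ongoing at a dose.
- Records per episode = 1 + number of severity changes (from the recording rule).
- TEAE window: from the period's dose to 5 days after it, with the earlier DB1 cut-off at the DB2 dose (SAP 6.2.5).
- Start date of a split record: not stated, so both options are traced.

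| History | Split record dated at the change | Split record keeps the original onset |
|---|---|---|
| A. Begins after the dose; mild, moderate, mild, all inside the window | 3 TEAE records | 3 TEAE records |
| B. Moderate before the DB1 dose; eases to mild within 5 days after it | 1 TEAE record in DB1 | none |
| C. Moderate, begins inside the DB1 window, still moderate at the DB2 dose; eases within 5 days after it | 1 in DB1 and 1 in DB2 | 2 in DB1, none in DB2 |
| D. Mild before the dose; resolves after it | none | none |

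**Case A.** Records = 1 + 2 = 3, and excess events = 3 − 1 = 2. This does not depend on how the records are dated. The subject count stays at 1 and the worst-severity table is unchanged, so only the frequency count is inflated.

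**Case B.** If an existing AE counts only on worsening, the correct count is 0. With dating at the change, the start-date limb gives 1. Overall subject incidence rises by one only if that subject has no other TEAE in the period.

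**Case C.** The correct count is 1, in DB1. Either dating option gives 2 records. With dating at the change, the second is a DB2 TEAE under the DB2 treatment, while the DB1 record remains where it was. The subject then also counts towards DB2 incidence, unless already counted there for another event.

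A severity change that occurs and is dated after the window produces no TEAE record.

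**The case against.** The best answer is that the SAP already excludes improvements. It supersedes the protocol where they differ (protocol 10.1). Its definition speaks of an AE, not a record, and deals with existing AEs in a limb that admits only worsening. If every worsening were already a new start, that limb would do no work, so the natural reading places existing AEs under the second limb. The site-facing definition points the same way: "any untoward event that started or worsened after the ICF was signed". The date of first occurrence could equally mean the original onset.

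This establishes the intent, and it means that the miscount in cases B and C is a possible result and not a stated one. It does not close the gap. The second limb adds cases and does not restrict the first. The protocol makes the split record a separate event, and a separate event that starts after dosing meets the first limb on its face. It also leaves case A untouched, where every record is a TEAE on either reading and no rule collapses them.

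Several limits on the exposure stand:
- The window is short.
- Anticipated fluctuations of pre-existing conditions "that do not represent a clinically significant exacerbation or worsening need not be considered AEs", which removes some of case B.
- Once-per-subject counting and worst-grade reporting protect the subject-level tables within a period.
- Case C needs an AE to persist from the DB1 dose, through Visit 3 (2 to 7 days after the treated attack), to the next treated attack, and then to ease within 5 days.

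**Conclusion.** The point holds as a defect in how the recording rule and the TEAE derivation fit together. It should be corrected before the TEAE tables are produced.

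- **Event counts.** Each severity change inside the window adds one TEAE to the frequency count. This follows directly from the text.
- **Subject-level incidence.** It can change only for a moderate or severe AE that is ongoing at a period's dose, eases within 5 days, and has its split record dated at the change. The documents do not allow the size to be derived.

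Four stronger readings may tempt a reader, and the documents do not support them.

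1. *An eased AE always becomes a new TEAE.* No section fixes the start date of a split record, so this is conditional.
2. *DB1 events are moved into the DB2 arm.* The original record stays a DB1 TEAE; at most a DB2 record is added to it.
3. *Incidence rises by 1 to 3 percentage points.* That figure assumes that 2% to 6% of 600 subjects (12 to 36) have an AE ongoing at the DB1 dose and that half of them (6 to 18) step down within 5 days; 6/600 = 1% and 18/600 = 3%. Neither assumption is in the documents. About 21 days of screening plus up to 28 days to treat the attack gives up to about 49 days of pre-dose collection, which shows only that such AEs are possible. The figure also ignores that a mild AE cannot step down and that a subject with another TEAE adds nothing. Its denominator is the number randomized, not the number dosed.
4. *The rule counts against DFN-15.* It applies to both blinded arms, no between-arm effect can be estimated from the documents, and migraine headaches are not captured as AEs.

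**What to change.** **Protocol 9.2.2.6 and the eCRF instructions.** Require a separate record only when severity increases. State that such a record starts on the date of the increase and that the earlier record stops then. When severity decreases, keep the existing record open with its original onset and maximum severity.

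**SAP 6.2.5 and 9.3.** Add a derivation rule along these lines, which also covers records already entered under the present instruction:
- A record opened because severity decreased is not a new TEAE.
- Contiguous records of the same preferred term that differ in severity count as one event with the earliest onset and the maximum severity. Contiguous means that the stop date of one equals, or is the day before, the start date of the next.
- That event is treatment-emergent in a period only if its onset, or an increase in its severity, falls in that period's window.

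**Cost.** One clarified sentence in the protocol and one derivation in the SAP. Preferred term, severity, and start and stop dates are already collected, so no new data are needed. The downside is a little more derivation work and a small risk of merging a true recurrence, which the contiguity condition limits. Collapsing on preferred term alone would carry a larger risk of that kind.
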